1.2.2.2. Nonclinical Toxicology

In the repeat-dose studies, the toxicity profile of GS-9876 was assessed in rats and monkeys administered GS-9876 orally for up to 26 weeks. Dose-dependent effects on lymphocytes in both rats and monkeys were consistent with the expected pharmacology of SYK inhibition. Effects on hemostasis were observed in rats and monkeys, with increased erythrocyte turnover in rats at ≥ 10 mg/kg/day, and hemorrhage and thrombosis in monkeys at ≥ 20 mg/kg/day. At higher doses in rats (≥ 30 mg/kg/day), mortality associated with bacterial infections, likely resulting from the immunomodulatory activity of GS-9876, was seen. Additional findings included lymphoid depletion in the thymus, changes in the pancreas, with secondary effects related to the immunomodulatory activity of GS-9876, and likely opportunistic bacterial infection, observed in several tissues. The no-observed-adverse-effect level (NOAEL) in rats was 10 mg/kg/day after 26 weeks dosing. For the 20 mg single dose proposed in this study, estimated exposure margins are 3.1-/7.6- fold based on exposures at the NOAELs in the 26 week study in male/female rats. Subjects will be closely monitored for any infection and changes in the differential CBC.

In monkeys, the NOAEL in the 28-day study was identified at 10 mg/kg/day, which was associated with AUC_{0-24hr} of 4290 ng•hr/mL. In the 13-week monkey study, there were no effects on hemostasis, and the NOAEL was the high dose of 15 mg/kg/day. In the 39-week monkey study, there was no evidence of effects on hemostasis at the high dose of 15 mg/kg/day, and the NOAEL was 15 mg/kg/day, associated with an AUC_{0-24hr} of 8040 ng•h/mL. For the 20 mg single dose proposed in this study, the estimated exposure margin is 2.8-fold based on exposures at the 15 mg/kg/day NOAEL in the 39-week monkey study.

In GLP range-finding developmental toxicity studies in pregnant rats and rabbits, no Caesarean-sectioning, litter parameters, or gross external or visceral alterations were affected by GS-9876 at dose levels up to 100 mg/kg/day in rats, or up to 30 mg/kg/day in rabbits. In rabbits at 100 mg/kg/day, mortality, clinical observations, reduced body weights and food consumption in does were associated with increased resorptions and reduced fetal body weights. In rats, the maternal no-observed-effect level (NOEL) was 30 mg/kg/day, and the embryo-fetal development NOEL was 100 mg/kg/day. In rabbits, the maternal and embryo-fetal development NOEL was 30 mg/kg/day.

GS-9876 was negative in the bacterial reverse mutation (Ames) assay, in vitro chromosomal aberration assay, and in vivo rat micronucleus assay and is therefore considered to be nongenotoxic. In the in vitro chromosome aberration assay in human lymphocytes, slight, but statistically significant increases in the number of polyploid cells was observed at the highest GS-9876 dose level evaluated. GS-9876 did not induce structural chromosome breakage when evaluated in the in vitro assay.

Table 1-1. Margins for GS-9876 Based on Systemic Exposure Relative to the Observed Human Exposure at 20 mg (AUC)

Species	Duration	Route	NOAEL (mg/kg/day)	AUC ₀₋₂₄ (ng•h/mL) ^a	Margin ^b
Rat	Once daily x 26 weeks	Oral	10	8800/21,800 (male/female)	3.1/7.6 (male/female)
Cynomolgus Monkey	Once daily x 39 weeks	Oral	15 ^c	8040	2.8

a NOAEL, no observed adverse effect level. Week 4 male and female rat AUC and week 13 Cynomolgus monkey AUC (combined sex)

b Margins of exposure were calculated using predicted 20 mg single dose exposure in humans of 2865 ng•h/mL (extrapolated from 30 mg single dose data in study GS-US-379-1372).

c One animal was euthanized moribund during Week 22 at the 15 mg/kg/day dose level.

1.2.2.3. Nonclinical Drug Metabolism and Pharmacokinetics

GS-9876 exhibits high absorption in rats, dogs and monkeys. Plasma protein binding is moderate in all species with the mean free fraction in humans being of 20.4%.

After oral dosing to albino and pigmented rats, [¹⁴C]GS-9876-derived radioactivity was rapidly distributed to most tissues and concentrations of radioactivity were below the limit of quantitation by 168 hours postdose. The lowest levels of radioactivity were observed in the brain, bone, adipose, and testis. Melanin containing tissues exhibited higher concentrations than their non-pigmented counterparts but binding was reversible. Recovery of radioactivity was high (≥ 97.8%) and the main route of elimination of GS-9876 was hepatobiliary with ≤ 5.1% orally dosed radioactivity found in urine and 69.4% in bile.

In vitro, GS-9876 exhibits high metabolic stability with human hepatocytes, liver fractions and individual metabolizing enzymes. GS-9876 had little inhibitory effect on the activities of the major human drug metabolizing CYP enzymes and was a weak inhibitor of human UGT1A1. GS-9876 is a weak inhibitor of P-gp and BCRP and is a substrate for those efflux transports. It is a weak inhibitor of the hepatic uptake transporters OATP1B1 and OATP1B3 but is a substrate for neither. Drug-drug interactions in vivo are unlikely through inhibition of human CYP enzymes, UGT1A1, or efflux or uptake transporters. The potential of GS-9876 to cause drug-drug interactions through induction is low as there is little activation of PXR or AhR in vitro.

1.2.3. Additional Clinical Studies of GS-9876

As of 12 February 2016, 62 healthy volunteers have been dosed with GS-9876 in two clinical studies.

1.2.3.1. Completed Clinical Trial

GS-US-379-1372: This was a first-in-human, Phase 1, single-dose ranging study of GS-9876 in healthy adult volunteers to evaluate the safety, tolerability, PK, PD, food effect, and drug-drug

interaction potential using a representative acid reducing agent (omeprazole). No risks were identified and no grade 3 or 4 AEs were reported. There were no clinically significant changes in vital signs, physical findings, bleeding times, or ECGs. For further information, refer to the current IB.

1.2.3.2. Ongoing Clinical Trials

GS-US-379-1582: This is a 12 week proof of concept trial of GS-9876 in patients with RA to evaluate efficacy, safety, tolerability and PK of GS-9876.

GS-US-379-1900: This is a single- and multiple-dose Phase 1 study of GS-9876 in healthy volunteers to evaluate the safety, tolerability, PK and PD of GS-9876. No risks were identified; all AEs were Grade 1 in severity. No dose relationships were observed between GS-9876 and any AE. No AE was assessed by the investigator as related to study drug. There were no clinically significant changes in vital signs, physical findings, laboratory parameters, or ECGs.

1.3. Rationale for This Study

Renal dysfunction may alter the elimination of drugs resulting in PK and subsequently pharmacodynamic changes. Available data indicate the disposition of GS-9876 is primarily via hepatic metabolism and elimination with minimal excretion expected in urine. In a nonclinical ADME study in rat (AD-379-2001), 2.7% to 5.1% of the administered radioactivity was excreted in urine. In study GS-US-379-1372 in humans, 0.6% to 4.1% of the dose of GS-9876 was excreted unchanged in urine following single oral doses from 2 to 50 mg. However, renal impairment may alter the disposition of hepatically cleared drugs due to possible changes in hepatic/gut drug metabolism, absorption and plasma protein binding. Thus, the objective of this study is to investigate the potential for clinically relevant alterations in the PK and safety of GS-9876 in subjects with renal impairment.

This study will be conducted in accordance with regulatory guidance and good scientific practice. This study will enroll subjects with moderate renal impairment (Cohort 1) with a screening estimated creatinine clearance (CL_{cr}) of 30-59 mL/min using the Cockcroft-Gault (C-G) equation for renal function as recommended by the Food and Drug Administration (FDA) and international guidance documents. Data from these subjects will be compared to matched subjects with normal renal function ($CL_{cr} \geq 90$ mL/min). Subjects with severe renal impairment (Cohort 2; CL_{cr} 15-29 mL/min) will be evaluated if supported by safety and/or PK data from Cohort 1. Should substantial changes in exposure be observed in Cohort 1, these data would inform the need for an expanded study including subjects with lesser degrees of renal dysfunction (Cohort 3; CL_{cr} 60-89 mL/min).

As renal impairment may be associated with changes in protein binding, a measurement of plasma protein binding will be conducted at or near T_{max} and at another later timepoint following GS-9876 dosing. Administration of GS-9876 as a single-dose is expected to accurately predict PK under steady-state conditions and is thus deemed satisfactory for evaluation in this study.

1.4. Rationale for the Dose Selection

The dose of GS-9876 to be used in this study is a 20 mg single dose in the fasted state. Results from study GS-US-379-1372 indicated that GS-9876 was safe and well tolerated when administered as a single dose of 2 mg to 50 mg. Similarly, preliminary results from study GS-US-379-1900 have indicated that GS-9876 was safe and well tolerated following 7 days dosing of GS-9876 15 mg QD, 30 mg QD or 50 mg QD. GS-9876 doses of 10 mg QD and 30 mg QD are currently under investigation in subjects with rheumatoid arthritis in study GS-US-379-1582. Thus a single dose of 20 mg GS-9876 represents a safe dose that's clinically relevant and allows for potential increase of GS-9876 exposures in subjects with renal impairment. Although food (high fat breakfast) only had minimal impact (reducing C_{max} by 13% and delaying T_{max} but no effect on AUC, on GS-9876 PK study GS-US-379-1372), GS-9876 will be administered in the fasted state in this study to avoid any potential confounding effect of food on assessing the effect of renal impairment on GS-9876 PK.

1.5. Risk/Benefit Assessment for the Study

While there is no direct benefit for the subject participating in the renal impairment study of GS-9876, the risks are considered to be minimal for the following reasons:

GS-9876 has been in a battery of nonclinical animal studies, and no renal toxicity was identified.

GS-9876 has been tested in humans as a single ascending dose over a dose range of 2 to 50 mg (GS-US-379-1372) and as a multiple ascending dose over a dose range of 15 to 50 mg (GS-US-379-1900) and no evidence of nephrotoxicity has been observed. In general GS-9876 was well tolerated at all dose levels. The planned single dose of 20 mg of GS-9876 is well below the highest dose given in the healthy volunteers and is expected to be tolerated well.

As discussed in Section 1.3, the disposition of GS-9876 is primarily via hepatic metabolism and elimination with minimal excretion expected in urine and the impact on renal impairment on GS-9876 PK is expected to be limited. Subjects in this study will receive a single 20 mg dose of GS-9876, which is expected to provide a margin of 2.8-fold to the NOAEL exposure in the 39-week Cynomolgus monkey toxicology study.

Evidence of deterioration in kidney function in humans can readily be detected and monitored using routine laboratory tests. For this study, frequent assessments of kidney function will be performed from the collection of both blood and urine samples. While subjects with renal impairment will be enrolled, the risk of further kidney injury in these subjects should be minimized by this close renal monitoring. Further, this study will enroll subjects with moderate renal impairment (Cohort 1) with a screening estimated creatinine clearance (CL_{cr}) of 30-59 mL/min first. Data from these subjects will be compared to matched subjects with normal renal function ($CL_{cr} \geq 90$ mL/min). Subjects with severe renal impairment (Cohort 2; CL_{cr} 15-29 mL/min) will only be evaluated if supported by safety and/or PK data from Cohort 1.

There are several potential causes of nephropathy in patients with chronic autoimmune diseases: primary autoimmune attack on the kidney, secondary renal amyloidosis, drug-related renal disease due to necessary drugs used to treat the primary autoimmune disease. Kidney disease and

impairment is thought to be highly prevalent in patients with autoimmune disease and therefore a renal impairment study is indicated and is in line with the FDA draft guidance Pharmacokinetics in patients with Impaired Renal Function indicating that a PK study in patients with renal impairment should be conducted for most drugs intended for chronic use.

The benefit-risk assessment for this study is favorable.

1.6. Compliance

This study will be conducted in compliance with this protocol, Good Clinical Practice (GCP), and all applicable regulatory requirements.

2. OBJECTIVES

The primary objective of this study is as follows:

- To evaluate the pharmacokinetics (PK) of GS-9876 in subjects with impaired renal function relative to matched healthy controls.

The secondary objective of this study is as follows:

- To evaluate the safety and tolerability of GS-9876 in subjects with normal and impaired renal function.

3. STUDY DESIGN

3.1. Study Design

This protocol describes a Phase 1, open-label, parallel-group, adaptive, single-dose, multi-center, pharmacokinetic study in subjects with renal impairment and matched healthy controls. A maximum of 60 subjects using an adaptive design that includes up to 3 enrolled cohorts.

- Cohort 1 (Moderate Renal Impairment): Up to 20 subjects (10 per group, moderate renal impairment and matched healthy controls) for 8 evaluable subjects per group.
- Adaptive Cohort 2 (Severe Renal Impairment): Up to 20 subjects (10 subjects with severe renal impairment and up to 10 matched healthy control subjects if none of the healthy subjects from a previous cohort is an appropriate match for a severe impairment subject) for 8 evaluable subjects per group.
- Adaptive Cohort 3 (Mild Renal Impairment): Up to 20 subjects (10 subjects with mild renal impairment and up to 10 matched healthy control subjects if none of the healthy subjects from a previous cohort is an appropriate match for a mild impairment subject) for 8 evaluable subjects per group.

Adaptive Cohorts 2 and/or 3 will be enrolled as determined by safety and/or PK data in Cohort 1. Specifically, Cohort 2 (Severe Renal Impairment) will be evaluated if supported by safety and/or PK data from Cohort 1 (Moderate Renal Impairment). Cohort 3 (Mild Renal Impairment) will be evaluated if supported by safety and if substantial changes (≥ 2 -fold mean difference from matched controls) in the exposure of GS-9876 is observed in subjects with moderate renal impairment in Cohort 1. Cohorts 2 and 3 may not be enrolled or may be enrolled sequentially or in parallel, as governed by safety and PK data in Cohort 1. Each control subject may be matched to multiple renal impaired subjects across different cohorts and can be matched to only 1 renal impaired subject within a cohort.

Male and nonpregnant, nonlactating female subjects 18 to 75 years of age, inclusive, with normal or impaired renal function will be enrolled into the study. Each subject in the control group will be matched for age (± 10 years), gender, and body mass index ($\pm 20\%$, ≥ 18 kg/m² and ≤ 36 kg/m²).

An overview of the study design is described below and shown in [Figure 3-1](#) and [Figure 3-2](#).

Figure 3-1. High Level Schema

[figure not shown]
[figure not shown]

Figure 3-2. Study Schema

3.2. Study Drug Administration

Following an overnight fast of at least 8 hours (no food or drink except water), study drug will be administered in the morning with 240 mL of water. Subjects will continue to fast until after collection of the 4-hour PK sample, relative to study drug dosing. Additionally, subjects will be restricted from water consumption 1 hour before until 2 hours after dosing, except for the 240 mL given with the study treatment.

Please refer to Section 5.3 for additional information for study drug dosage and administration.

3.3. Clinic Confinement

Following screening and Day -1 procedures, eligible subjects will be confined to the study center beginning Day -1 until completion of assessments on Day 6. Subjects will return 14 (\pm 1) days after last dose for an in-clinic follow up visit (ie. Day 15).

3.4. Pharmacokinetic Assessments

Pharmacokinetic assessments will occur on assigned study days as outlined in [Table 6-1](#) and [Section 6.7](#).

3.4.1. Plasma Pharmacokinetic Collection

Plasma concentrations of GS-9876 will be measured and PK parameters determined. Plasma concentrations of GS-9876 metabolites may be determined and pharmacokinetics explored, as applicable.

3.4.2. Urine Pharmacokinetic Collection

All urine voided will be collected and pooled for the determination of PK parameters as outlined in Section 6.8.2. Urine concentrations of GS-9876, as well as its metabolites, may be analyzed.

3.5. Safety Assessments

Safety assessments will be performed through the study as outlined in Table 6-1 and in Section 6.9.

3.6. End of Study

The end of this study will be the last subject's last observation (or visit).

4. SUBJECT POPULATION

4.1. Number of Subjects and Subject Selection

A total of up to 60 subjects will be enrolled in the study (up to 20 subjects per cohort), consisting of healthy male and nonpregnant, nonlactating female subjects of 18 through 75 years of age, inclusive. If necessary, replacement subjects may be enrolled if subjects do not complete all intensive PK procedures with sponsor approval. Replacement subjects will not be enrolled for subjects who discontinue the study due to study drug-related AEs. Each control subject may be matched to multiple renal impaired subjects across different cohorts and can be matched to only 1 renal impaired subject within a cohort.

Subjects will comprise those with normal and impaired renal function. Those with impaired renal function will be categorized based on estimated creatinine clearance (CL_{cr}) using the Cockcroft-Gault (C-G) equation for renal function as recommended by the Food and Drug Administration (FDA) and international guidance documents. Classification of renal impairment is defined as follows:

- Mild: CL_{cr} 60-89 mL/min
- Moderate: CL_{cr} 30-59 mL/min
- Severe: CL_{cr} 15-29 mL/min

Severe renal impairment subjects requiring or anticipated to require dialysis within 90 days of study entry are not eligible. The control group will consist of matched control subjects with normal renal function ($CL_{cr} \geq 90$ mL/min).

Each subject in the control group will be matched for age (± 10 years), gender, and body mass index ($\pm 20\%$, ≥ 18 kg/m² and ≤ 36 kg/m²).

4.2. Inclusion Criteria

Subjects must meet all of the following inclusion criteria to be eligible for participation in this study:

4.2.1. All Subjects

- 1) Have the ability to understand and sign a written informed consent form (ICF), which must be obtained prior to initiation of study procedures
- 2) Be between 18 through 75 years of age, inclusive at screening
- 3) Must be able to comply with the smoking restrictions at the study site.
- 4) Have a calculated body mass index (BMI) of ≥ 18 kg/m² and ≤ 36 kg/m² at screening

- 5) Females of childbearing potential (as defined in [Appendix 3](#)) must have a negative serum pregnancy test at screening and clinic admission (Day -1).
- 6) Female subjects must refrain from egg donation and in vitro fertilization during treatment and until at least 36 days after the last dose of study drug.
- 7) Male subjects and female subjects of childbearing potential who engage in heterosexual intercourse must agree to use protocol specified method(s) of contraception as described in [Appendix 3](#).
- 8) Male subjects must refrain from sperm donation from clinic admission (eg, Day -1), throughout the study period, and continuing for at least 90 days following the last dose of study drug
- 9) Subjects have not donated blood within 56 days of study entry or plasma within 7 days of study entry and must refrain from blood donation from clinic admission, throughout the study period, and continuing for at least 30 days following the last dose of study drug.
- 10) Have either a normal 12-lead ECG or one with abnormalities that are considered clinically insignificant by the investigator in consultation with the sponsor
- 11) Must be willing and able to comply with all study requirements
- 12) Must, in the opinion of the investigator, be in good health based upon medical history and physical examination, including vital signs
- 13) Subjects must have the following laboratory parameters at screening:
 - a) Hemoglobin ≥ 8.0 g/dL (International System of Units [SI]: ≥ 80 g/L)
 - b) White blood cells $\geq 3.0 \times 10^3$ cells/mm³ (SI: $\geq 3.0 \times 10^9$ cells/L)
 - c) Neutrophils $\geq 1.5 \times 10^3$ cells/mm³ (SI: $\geq 1.5 \times 10^9$ cells/L)
 - d) Lymphocytes $\geq 0.5 \times 10^3$ cells/mm³ (SI: $\geq 0.5 \times 10^9$ cells/L)
 - e) Platelets $\geq 100 \times 10^3$ cells/mm³ (SI: $\geq 100 \times 10^9$ cells/L)
 - f) Alanine aminotransferase (ALT) or aspartate aminotransferase (AST) $< 1.5 \times$ ULN
 - g) Total bilirubin level $< 2 \times$ ULN

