4.3. Exclusion Criteria

4.3.1. All Subjects

Subjects who meet *any* of the following exclusion criteria will not be enrolled in this study:

- 1) Be a lactating female

- 2) Have received any investigational compound within 30 days prior to study dosing
- 3) Have current alcohol or substance abuse judged by the investigator to potentially interfere with subject compliance or subject safety as judged by the investigator
- 4) Have a positive test result for human immunodeficiency virus type 1 (HIV-1) antibody, hepatitis B surface antigen (HBsAg), hepatitis B core antibody (HBcAb), or hepatitis C virus (HCV) antibody
- 5) Have poor venous access that limits phlebotomy
- 6) Have been treated with systemic steroids, immunosuppressant therapies, or chemotherapeutic agents within 3 months prior to screening or is expected to receive these agents during the study (eg, corticosteroids, immunoglobulins, and other immune- or cytokine-based therapies)
- 7) Have a history of any of the following:
 - a) Significant serious skin disease, such as but not limited to rash, food allergy, eczema, psoriasis, or urticaria
 - b) Significant drug sensitivity or drug allergy (such as anaphylaxis or hepatotoxicity)
 - c) Known hypersensitivity to the study drugs, their metabolites or to formulation excipients (see Section 5)
 - d) Significant cardiac disease (including history of myocardial infarction based on ECG and/or clinical history, any history of ventricular tachycardia, congestive heart failure, or dilated cardiomyopathy with left ventricular ejection fraction < 40%), a family history of long QT syndrome, or unexplained death in an otherwise healthy individual between the ages of 1 and 30 years
 - e) Syncope, palpitations, or unexplained dizziness
 - f) Implanted defibrillator or pacemaker
 - g) Liver disease, including Gilbert disease
 - h) Severe peptic ulcer disease, gastroesophageal reflux disease, or other gastric acid hypersecretory conditions requiring prolonged (> 6 months) medical treatment.
 - i) Medical or surgical treatment that permanently altered gastric absorption (eg, gastric or intestinal surgery). A history of cholecystectomy is not exclusionary.
 - j) History of any major bleeding event defined as Grade 3 severity and above (as defined by the modified CTCAE 4.03[[Appendix 4](#)]) within the last year or personal or family history of bleeding disorder

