 - k) Current use of chronic anticoagulant or anti-platelet agent, not including daily aspirin for cardiac prophylaxis.

- 8) Have any serious or active medical or psychiatric illness (including depression) that, in the opinion of the investigator, would interfere with subject treatment, assessment, or compliance with the protocol. This would include cardiac, hematological, hepatic, pulmonary (including chronic asthma), endocrine (including diabetes), central nervous, gastrointestinal (including an ulcer), vascular, metabolic (thyroid disorders, adrenal disease), immunodeficiency disorders, active infection, or malignancy that are clinically significant or requiring treatment.
- 9) Recent significant changes in the use of nicotine or nicotine containing products (ie, initiation, substantial increase or decrease or cessation of use) in the 90 days prior to study drug dosing, or anticipated significant changes in the use of nicotine or nicotine containing products during the course of the study through the follow-up visit.

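### Inclusion criterion 13(f) joins ALT and AST with 'or', so one enzyme below the limit satisfies it and no other criterion sets a transaminase limit

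*Protocol*

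**What the plan says.** Protocol section 4.2 opens with "Subjects must meet all of the following inclusion criteria to be eligible for participation in this study". Within section 4.2.1, criterion 13 lists laboratory parameters required at screening for impaired and control subjects alike. Item (f) is "Alanine aminotransferase (ALT) or aspartate aminotransferase (AST", with a limit of less than 1.5 × ULN. Item (g), "Total bilirubin level", has a limit of less than 2 × ULN.

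Other eligibility text also bears on the liver:

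- Inclusion 12 asks that the subject, in the investigator's opinion, "be in good health based upon medical history and physical examination, including vital signs".
- Exclusion 4 (section 4.3.1) removes subjects positive for "hepatitis B surface antigen (HBsAg), hepatitis B core antibody (HBcAb), or hepatitis C virus (HCV) antibody".
- Exclusion 7(g) removes a history of "Liver disease, including Gilbert disease".
- Exclusion 8 removes serious or active illness that the investigator thinks would interfere with the study. Its list begins "This would include cardiac, hematological, hepatic, pulmonary (including chronic asthma" and is limited to conditions that are clinically significant or need treatment.
- Section 6.2.2.1 has the investigator review clinical and laboratory results before dosing to confirm continued eligibility.

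On the drug, section 1.3 says "the disposition of GS-9876 is primarily via hepatic metabolism and elimination with minimal excretion expected in urine", and reports 0.6% to 4.1% of the dose recovered unchanged in human urine.

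**The concern.** In an exclusion list, 'ALT or AST above the limit' removes anyone with either enzyme raised. In a list of required values, 'ALT or AST below the limit' admits anyone with either enzyme acceptable. Item 13(f) has the second form, so taken literally it stops only subjects in whom both enzymes are at or above 1.5 × ULN.

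Three things are at stake.

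- **Safety screening.** A subject with one markedly raised transaminase can meet the only transaminase criterion in the protocol and be dosed. SAP section 7.2.2.1 counts a laboratory abnormality as treatment-emergent only if it rises at least one grade from predose. A subject who enters with a graded elevation must worsen further to be counted.
- **Interpretation.** Liver function is a plausible non-renal influence on AUC and Cmax for this drug. Controls are matched on age, gender and BMI only (Protocol 4.1). The SAP uses no covariates (3.2), and its PK model contains renal function group alone (8.2.2). An imbalance in liver status would not be adjusted for.
- **Visibility.** SAP section 4.3 lists subjects who failed an eligibility criterion. Under the literal reading this subject failed none. With centers planned in three countries, sites could also read the item differently.

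**Working it through.** **1. The plan's own figure.** Inputs from Protocol 8.8: 8 evaluable subjects per group, ln-scale SD 0.35, true ratio 1.0, bounds 50% and 200% (±ln 2 = ±0.693), and each one-sided test at 0.05. The standard error of the ln ratio is 0.35 × √(2/8) = 0.175. The exact power of two one-sided tests with pooled variance on 14 degrees of freedom is 96.6%. The normal approximation, 2Φ(0.693/0.175 − 1.645) − 1, gives 97.9%. The stated probability of over 95% is reproduced, and the wording of 13(f) does not enter it.

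**2. Item 13(f) as logic.**

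| ALT (× ULN) | AST (× ULN) | 'or' (as written) | 'and' |
|---|---|---|---|
| 1.0 | 1.4 | pass | pass |
| 5 | 1.4 | pass | fail |
| 1.0 | 5 | pass | fail |
| 3 | 3 | fail | fail |

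The two readings differ exactly where one enzyme is raised and the other is not.

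**3. Do the other criteria stop that subject?**

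| Provision | What it tests | Transaminase limit? |
|---|---|---|
| 13(g) | total bilirubin | no |
| Inclusion 12 | history, examination, vital signs; investigator opinion | no |
| Exclusion 4 | hepatitis B and C serology (and HIV-1) | no |
| Exclusion 7(g) | history of liver disease | no |
| Exclusion 8 | clinically significant hepatic illness; investigator opinion | no |
| 6.2.2.1 | pre-dose review of results for continued eligibility | no limit of its own |

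A subject with one raised enzyme, normal bilirubin, negative serology and no diagnosed liver disease passes every numeric and serological test. Exclusion then depends on the investigator's judgement.

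**4. Possible size in the PK comparison.** The documents give no hepatic-impairment data and no link between transaminases and GS-9876 exposure, so the fold changes f below are assumptions. If k of 8 subjects in one group have exposure multiplied by f, that group's geometric mean is multiplied by f^(k/8). For example, 2^(1/8) = exp(0.693/8) = 1.09. The last column repeats the calculation in step 1 with the shifted ratio and the SD held at 0.35.

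| f | k | Factor on group geometric mean | Probability 90% CI within 50%–200% |
|---|---|---|---|
| none | 0 | 1.00 | 96.6% |
| 1.25 | 1 | 1.03 | 96.4% |
| 1.25 | 2 | 1.06 | 95.7% |
| 1.5 | 1 | 1.05 | 95.9% |
| 1.5 | 2 | 1.11 | 93.8% |
| 2 | 1 | 1.09 | 94.5% |
| 2 | 2 | 1.19 | 87.9% |

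At f = 3 the factors are 3^(1/8) = 1.15 and 3^(2/8) = 1.32. An affected subject in the impaired group raises the ratio; one in the control group lowers it by the same factor. If all 10 enrolled per group contribute, the 2-fold factors fall to 2^(1/10) = 1.07 and 2^(2/10) = 1.15.

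**5. Against the Cohort 3 trigger.** Section 3.1 opens Cohort 3 at a mean difference of at least 2-fold. If that is read on geometric means, one impaired subject with doubled AUC could carry the estimate over the trigger only when the ratio would otherwise lie between 2/1.09 = 1.83 and 2.

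**The case against.** The strongest reply is that the other criteria do most of the work. All inclusion criteria must be met, so passing 13(f) is not the same as qualifying. Serology, liver-disease history, bilirubin and good health all apply. So do the alcohol and substance-abuse exclusion, with urine screens at screening and Day -1, and the medication rules. The investigator must review the laboratory results before dosing and can use exclusion 8. This stands as far as it goes: a reader who infers that such a subject is simply eligible goes further than the text allows. But each of these either tests something else or rests on judgement, so the gap is narrowed and not closed.

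A reader might also infer that the renal comparison is confounded. The documents do not support that. None of them links a raised ALT or AST to GS-9876 exposure, and a transaminase is not a measure of hepatic clearance. The criterion applies equally to both groups, and nothing in the documents says how often an isolated elevation would occur. Equal wording does not guarantee balance, since impaired subjects may take stable medication for other diseases while controls mostly may not. That, however, is inference and not evidence of a directional bias.

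Finally, 'or' may be loose drafting for 'neither enzyme above the limit', and sites may read it so. The text does not settle this. An eligibility rule should not depend on guessing, so the possibility supports clarifying the item.

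**Conclusion.** The point holds as a drafting fault in an entry criterion that governs every subject. Read literally, 13(f) is met by one enzyme, no other provision sets a transaminase limit, and a subject with one markedly raised transaminase could still be enrolled and dosed. The main consequence is a weaker liver-safety screen.

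The consequence for the PK result is possible, not shown, and probably small. One affected subject of 8 moves a group geometric mean by about 1.09 and lowers the stated probability from 96.6% to 94.5%. Two move it by 1.19 and lower the probability to 87.9%. These figures rest on an assumed doubling of AUC, an unchanged SD of 0.35 and all affected subjects falling in the same group. No figure in the sample-size section is wrong.

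A reader might also conclude that a numeric transaminase test is needed at Day -1. The documents do not call for it: criterion 13 is set at screening, and section 6.2.2.1 already requires a review of Day -1 results.

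**What to change.** Reconcile 13(f) with its apparent purpose by stating that the sponsor's existing limit must be met by both enzymes: ALT and AST each below 1.5 × ULN at screening. The threshold and the timing stay as they are.

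The cost is a short wording change in a protocol amendment. No test is added, because both enzymes are in the chemistry panel (section 6.9.5.1), which is already run at screening (Table 6-1). Sample size, model and SAP text are unaffected. If some sites have read 13(f) literally, a few more screen failures may follow; the documents give no basis for estimating how many.
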